5.3.3 Main Analytical Approach for Primary Endpoint

Descriptive summary statistics for the brain amyloid CL load at baseline, Week 52 and Week 104 as well as the change from baseline to Week 52 and to Week 104 will be produced on both the ITT and Amyloid-PET-longitudinal analysis sets. Descriptive summaries of the primary endpoint will present the mean, standard deviation, median, and minimum and maximum.

A Mixed Model for Repeated Measures (MMRM) analysis will be used to estimate the mean change in CL from baseline to Week 52 and to Week 104 on the ITT analysis set. The model will include the change from baseline in CL as the dependent variable, while adjusting for visit (as categorical), apolipoprotein E allele $\epsilon 4$ (APOE $\epsilon 4$) status (as categorical; carrier vs non-carrier), baseline CL, and baseline CL-by-visit. Visit will be treated as the repeated variable within a participant. An unstructured variance-covariance matrix will be applied to model the within-participant errors; in the case of non-convergence, compound symmetry will be used, together with a robust estimator of standard error ("sandwich" estimator).

In line with the primary estimand definition, data acquired after the ICE "Substantial reduction in drug exposure due to the COVID-19 pandemic" (as defined above) or more than 56 days from date of last dose will be excluded from the analysis and treated as missing for the primary analysis purposes.

There will be no data imputation for missing data. However, the MMRM model provides unbiased estimates and valid inference in the presence of missing data, under the MAR (missing at random) assumption.

The least squares means at Week 52 and at Week 104 will be estimated and presented with a 95% CI.

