4.5.5 Positron Emission Tomography Scan

Two radioligands may be used in this study: florbetaben for participants at all sites (in exceptional circumstances, the use of flutemetamol may be acceptable at sites where florbetaben is not available, but only after prior written approval from the Sponsor).

Screening PET scans must not be acquired prior to the availability of potentially exclusionary screening results in order to minimize radiation burden to participants. To allow sufficient flexibility for scheduling of the screening PET scan, screening procedures (including central reading of the MRI scans) ideally should be completed within 2–3 weeks before the screening PET scan is required.

A positive PET scan using any amyloid tracer, acquired outside this study protocol is not permissible to confirm participant inclusion due to the longitudinal PET imaging requirements for all subjects enrolled in this study.

After obtaining the signed Informed Consent Form at the clinical study site, the following assessments and procedures will be performed for all participants during each amyloid PET scanning session:

- The responsible physician or his or her designee at the PET imaging center will confirm a participant's suitability for undergoing the PET imaging after a brief medical assessment, which may include weight. The PET scan should not be performed if the participant has an ongoing ARIA-E.
- For women of childbearing potential (including those who have had a tubal ligation), a urine pregnancy test will be conducted within 24 hours before the PET scan. The result must be negative for the participant to receive the amyloid tracer.
- The participant must void his or her bladder prior to scanning.
- Placement of an IV catheter into a forearm or antecubital vein for the injection of the investigational PET tracer must occur.
- A target dose of 300 [\pm 10%] MBq for florbetaben or 185 [\pm 10%] MBq for flutemetamol will be administered intravenously as a single slow bolus. The cannula

will be immediately flushed with up to 5–15 mL of saline solution. It is recognized that due to scheduling, transit, or manufacturing issues, from time to time, it is possible that an imaging center may be delivered a dose of amyloid radioligand that is less than the target dose. In these cases, participants may still be injected. However, if the dose is < 70% of the target dose, no injection should be performed and the participant should be rescheduled for imaging.

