- Additional measures for nonclinical administration by study partner (non-professional caregiver): Every 4 weeks, except when there is an in-person clinic visit, the investigator or an appointed qualified study staff will have a telephone conversation with the participant and/or study partner (non-professional caregiver) to elicit, in a non-leading way, information on medication errors and adverse events that may have occurred in the home setting. Therefore, there will be frequent contact between the study staff and the participant/study partner (non-professional caregiver). In addition, participants/study partners (non-professional caregivers) will be instructed to contact the investigator and seek approval for continued study drug dosing in the home setting in case of onset of any new symptoms or symptom worsening. These requirements will aid symptomatic ARIA-E detection and dose intervention, as described below, in the case of an asymptomatic ARIA-E that becomes symptomatic at a later date.

If BGTS ≥ 4 or symptoms develop, refer to the rule below.

- In case of occurrence of symptoms in the presence of ARIA-E (any size) or asymptomatic ARIA-E with BGTS ≥ 4 : Temporarily interrupt study drug (but continue all assessments per schedule of activities) and perform MRI monitoring at 4-week intervals until symptoms and ARIA resolve.

When symptoms and ARIA-E resolve, reintroduce study drug at the next scheduled dosing visit, at the same dose given at the time the event was detected.

Perform an MRI scan after the first dose while participants are on a Q4W dosing frequency, or after the second dose while participants are on a Q2W dosing frequency, or after the third or fourth dose while participants are on a Q1W dosing frequency.

If no new ARIA-E is detected, resume uptitration and obtain an MRI per the titration schedule. For participants on the Q1W dosing frequency, perform another MRI scan 3 months after study drug reintroduction.

- The investigator may choose to perform additional MRI monitoring for ARIA at any time.
- Symptomatic ARIA-E is defined as onset or worsening of CNS symptom(s) that is/are temporally associated with ARIA-E MRI findings.
- Any recurrence of ARIA-E: Treat using the same procedures as for the first event (based on symptoms and BGTS).

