The study will consist of a screening period of up to 8 weeks for each participant who agrees to participate, signs the Informed Consent Form, and is eligible for the study. Eligible participants will then undergo the baseline visit (Day 1), when they will receive the first dose following completion of all relevant assessments. Participants will be enrolled in an open-label treatment period of up to 208 weeks. The PET scans will be performed at screening (will be considered as baseline evaluation), Weeks 52, 104, 156, and 208 using florbetaben as the tracer at all sites (in exceptional circumstances, the use of flutemetamol may be acceptable at sites where florbetaben is not available, but only after prior written approval from the Sponsor). Participants will be treated according to the following dosing regimen: 120 mg Q4W (Day 1, Week 4, and Week 8), then 255 mg Q4W (Weeks 12, 16, and 20), and then 255 mg Q2W for 12 weeks (Weeks 24, 26, 28, 30, 32, and 34), followed by the target dose 255 mg Q1W (Weeks 36–207). Before reaching the target dose (i.e., 255 mg Q1W), a minimum of three doses during the 120 mg Q4W and 255-mg Q4W dosing periods, and a minimum of six doses during 255 mg Q2W dosing period must be administered prior to uptitration. Participants who do not opt for the two-year extension of GRADUATION, will receive the final dose of study drug at Week 103. Final PD and efficacy assessments will be performed 1 week later at Week 104. Participants who do not enter an extension study will have an additional follow-up visit 16 weeks after the Week 104 visit for safety assessments (Week 120 follow-up visit). Participants who opt for the two-year extension of GRADUATION will receive the final dose of study drug at Week 207. Final PD and efficacy assessments will be performed one week later at Week 208. Eligible participants may qualify for continued access or ongoing extension studies as outlined in the Protocol (version 3.0), Section 4.3.5. Participants who do not enter an extension study will have an additional follow-up visit 16 weeks after the Week 208 visit for safety assessments (Week 224 follow-up visit).

Depending on the site and individual participant/caregiver suitability, participants will have the option to receive SC injections of gantenerumab at the site or at home by study staff, a home nurse, or a study partner (non-professional caregiver) after a defined

Gantenerumab—F. Hoffmann-La Roche Ltd

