5.1.1 Visit Windowing

The analysis of data will be undertaken using reporting windows. As all the endpoints in the study are collected at different time frequencies, different sets of reporting windows will be applied depending on the frequency of assessments. In case of more than one assessment within a time window, the assessment with the date closest to the target (scheduled) day will be selected.

For amyloid PET assessments, time windows will be used ([Table 2](#)). Because of visit windowing, data collected at an early termination visit will be summarized at the appropriate time in the trial. For participants who have discontinued treatment early, if a PET scan is performed more than 56 days after the date of last dose, the PET scan will not be used for the analysis.

Table 2 Time Windows for Amyloid PET Endpoints

Visit	Target study day	Time window
Baseline	1	Up to day 1
Week 52	365	281, 449
Week 104	729	645, 813

For endpoints of home administration questionnaire (Caregiver or Patient), time windows will be applied ([Table 3](#)).

Table 3 Time Windows for Home Administration Questionnaire Endpoints

Visit	Target study day	Time window
Baseline	- (no baseline assessment planned)	- (no baseline assessment planned)
Week 36	253	2, 308
Week 52	365	309, 448
Week 76	533	449, 630
Week 104	729	631, 770

For cognitive and functional endpoints, time windows will be applied ([Table 4](#))

Table 4 Time Windows for Cognitive and Functional Endpoints

Visit	Target study day	Time window
Baseline	1	Up to Day 1
Week 24	169	2, 266
Week 52	365	267, 448
Week 76	533	449, 630
Week 104	729	631, 770

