5.3.2 Definition of Primary Estimand

The scientific question of interest is to assess the effect of the intended study treatment on the PD endpoint, change from baseline to Week 104 in brain amyloid load, in participants treated with SC gantenerumab, in the absence of a substantial impact of the COVID-19 pandemic and as if treatment discontinuation would not have occurred.

In alignment with the Addendum to ICH E9, the primary Amyloid PET estimand is thus described by the following attributes:

- **Target Population:**
Early (prodromal to mild) AD population as identified by the inclusion and exclusion criteria, see the Protocol (version 3.0), Sections 4.1.1 and 4.1.2
- **Variable:**
Change from baseline to Week 104 in amyloid PET CL
- **Treatment:**
Prescribed study drug in a Q1W regimen, including up-titration to the target dose
- **Population-level summary:**
Variable mean in the ITT analysis set
- **Intercurrent events (ICEs):**
 - Substantial reduction in drug exposure due to the COVID-19 pandemic (defined as ≥ 4 missed dose-months)
 - Treatment discontinuation due to any reason

Considering that amyloid PET primarily aims at estimating the Pharmacodynamic effect of the drug, rather than a direct measure of clinical efficacy, reporting treatment effect estimated "as if there were no treatment discontinuations and no substantial reduction in exposure due to COVID-19 pandemic" (thus using a hypothetical strategy) addresses the scientific question of interest.

The ICE of substantial reduction in drug exposure due to the COVID-19 pandemic is defined as 4 or more dose-months (i.e., 16 weeks) of treatment missed due to COVID-19-related reason. One dose-month is defined as 4 weeks of dosing, i.e., one dose with a Q4W dosing frequency or two doses with a Q2W dosing frequency or four doses with a Q1W dosing frequency (at target dose). The threshold (4) on the number of missed dose-months was determined based on the following reasons:

- Based on the half-life of approximately 24 days of gantenerumab, plasma concentrations after 4 months' interruption at the target dose are expected to be below the concentration with the dose of 225 mg Q4W which was shown to be ineffective in SCarlet RoAD and Marguerite RoAD
- Comparability to the GRADUATE I and GRADUATE II studies which use the same cut-off.

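### SAP 5.3.3 states the 56-day post-dose PET exclusion for everyone, while SAP 5.1.1 limits it to early discontinuers, so a few in-window primary-endpoint scans could be dropped with no listed intercurrent event

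*SAP*

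**What the plan says.** - **Estimand (SAP 5.3.2).** There are two intercurrent events, both handled by a hypothetical strategy. One is "4 or more dose-months (i.e., 16 weeks) of treatment missed due to COVID-19-related reason". The other is "Treatment discontinuation due to any reason". A temporary interruption for any other reason is not listed.
- **Windowing (SAP 5.1.1).** "For participants who have discontinued treatment early, if a PET scan is performed more than 56 days after the date of last dose", the scan is not used. Table 2 sets the Week 104 window at Days 645 to 813 and the Week 52 window at Days 281 to 449.
- **Primary analysis (SAP 5.3.3).** "In line with the primary estimand definition, data acquired after the ICE" of COVID-19 exposure loss, "or more than 56 days from date of last dose will be excluded from the analysis and treated as missing for the primary analysis purposes". The 56-day limb is not restricted to participants who discontinued.
- **Last dose.** Neither section says whether this is the final dose in the study or the latest dose before the scan.
- **Dosing (SAP 1.2).** Participants who do not take up the extension "will receive the final dose of study drug at Week 103". Extension participants keep dosing at Week 104 and beyond (Protocol Appendix 1, Table 5).
- **ARIA-E holds (Protocol 5.1.3.1).** For symptomatic ARIA-E or a BGTS of 4 or more, the instruction is: "Temporarily interrupt study drug (but continue all assessments per schedule of activities) and perform MRI monitoring at 4-week intervals until symptoms and ARIA resolve". Protocol 4.5.5 adds: "The PET scan should not be performed if the participant has an ongoing ARIA-E".

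**The concern.** The 56-day rule decides which scans enter the primary MMRM, and the SAP states it in two ways. A programmer working from 5.1.1 and one working from 5.3.3 could build different primary data sets. The Week 52 interim estimate is exposed too, because SAP 5.8.1 sends it to Section 5.3.

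The wider version is the one that claims to follow the estimand, yet it can remove scans from participants who have had neither listed event. For completers, keeping a late scan would then depend on whether they consented to an optional extension. Because the study is open-label, settling the question after lock would mean choosing with the data in view.

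**Working it through.** **1. Reproduce Table 2.** Study day = 7 × week + 1.
- Week 52: 7 × 52 + 1 = 365; 365 ± 84 = 281 to 449.
- Week 104: 7 × 104 + 1 = 729; 729 ± 84 = 645 to 813.

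Both match, and each window is 169 days long.

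**2. Completers outside the extension.**
- Last dose at Week 103: 7 × 103 + 1 = Day 722.
- Last day allowed by 5.3.3: 722 + 56 = Day 778.
- Scans on Days 779 to 813 are inside Table 2, kept by 5.1.1 and dropped by 5.3.3. That is 813 − 778 = 35 of 169 days. With the ±3-day dosing window on the last dose it is 32 to 38 days.
- An extension participant scanned on the same day keeps the scan under either meaning of last dose.

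**3. How late such a scan must be.** It must come at least 779 − 729 = 50 days after target. The schedule of activities lets PET run up to 4 weeks late in exceptional circumstances, about Day 757. That is 757 − 722 = 35 days after the last dose, or at most 41 with 3-day shifts on both sides. Scans within that allowance are safe.

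**4. Interruptions, if last dose means the latest dose before the scan.**
- On-time Week 104 scan (Day 729): latest dose at Week 96 (Day 673) gives a gap of 56 days, kept. Latest dose at Week 95 (Day 666) gives 63 days, dropped. So at least 8 weekly doses must be missed.
- On-time Week 52 scan (Day 365): dropped if the latest dose was at Week 43 (Day 302, gap 63 days) or earlier.
- If last dose means the final dose in the study, anyone who restarts keeps the scan. The two meanings coincide only where an interruption runs to the end of treatment in someone outside the extension.

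**5. Conflict with the COVID-19 threshold.** Four dose-months = 4 × 28 = 112 days; 56 days = 2 dose-months. Under the latest-dose meaning, a COVID-19 run of 8 to 15 missed weekly doses just before an on-time scan (gap 63 to 112 days) is below the threshold of 16 weekly doses. Section 5.3.2 therefore retains the scan, but the 56-day clause removes it. In SAP 5.3.4 the 5- and 6-dose-month analyses leave the rest of the estimator unchanged, so they would not restore it. The analysis that ignores COVID-19 impact does not say that it lifts the 56-day clause.

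**6. Effect on precision (illustration only).** Half-width = 1.96 × 25.67 / √n. With the SAP's roughly 35% loss, n = 0.65 × 192 = 124.8. The extra losses are assumed.

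| Extra scans lost (assumed) | n | 95% CI half-width, CL |
|---|---|---|
| 0% | 124.8 | 4.50 |
| 2% | 122.3 | 4.55 |
| 5% | 118.6 | 4.62 |
| 10% | 112.3 | 4.75 |

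**The case against.** The strongest reply is that the two sections can be read together. Section 5.3.3 says it follows the estimand and has two limbs for two intercurrent events. The first names COVID-19, so the second must implement discontinuation, which 5.1.1 spells out. The adverse-event rule in SAP 5.6.2, which counts 17 weeks from last dose, also suggests the final dose. This is probably what was intended, and it supports restoring the 5.1.1 restriction. It does not make 5.3.3 say so, and a program is written from the text.

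It is also fair that the completer zone is nearly empty, since scans there fall outside the protocol's own allowance. That allowance limits how many such scans will exist. It does not decide inclusion, because Table 2 accepts scans to Day 813.

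A reader might infer something stronger: that with a predicted ARIA-E rate of about 26% (Protocol 3.3.1), 5.3.3 turns ARIA-E holds into a sizeable unlisted event and biases the mean toward greater amyloid removal. The documents do not support that.
- PET is barred while ARIA-E is ongoing, and dosing resumes at the next scheduled dosing visit once symptoms and ARIA-E have resolved. That visit is weekly at target dose, so most scans after a hold would follow a recent dose.
- What remains is narrow: ARIA-E resolved but dosing not yet restarted, symptoms outlasting the imaging finding, or a hold running to the end of treatment outside the extension.
- Participants who restart are caught only under the latest-dose meaning.
- Nothing in the documents gives the share of holds that overlap a PET visit, or how far those scans differ in CL.

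**Conclusion.** Wrong as written. The mismatch is on the page, and the day arithmetic shows that 5.3.3 can remove in-window primary-endpoint scans when neither listed event has occurred. The completer case (Days 779 to 813) holds under either meaning of last dose. The interruption and sub-threshold COVID-19 cases for participants who restart require the latest-dose meaning.

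Few scans are likely to be affected, and the documents do not allow a count. If 2% to 10% were lost, the half-width would rise by 0.05 to 0.25 CL, against a predicted Week 104 reduction of about 67 CL (Protocol 3.3.5). That covers precision only. Dropping lower-exposure scans could make the mean reduction look larger, but this direction is plausible rather than shown, and it need not apply to completers who were simply scanned late. No hypothesis is tested. The case for acting is a single, reproducible definition of the primary data set, not a material change in the result.

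**What to change.** In SAP 5.3.3, replace the 56-day clause with: *or, in participants who permanently discontinued study treatment early, more than 56 days after their final dose (as in Section 5.1.1)*. Then add: *All other scans inside the Table 2 window are kept unless the COVID-19 intercurrent event has occurred.*

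The last condition is needed. A statement that every scan after a temporary interruption is kept would override the COVID-19 event, since an interruption of 16 weeks or more for that reason is itself temporary.

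Naming the final dose settles the undefined term and aligns the two sections. The cost is one amended clause and one added sentence, best made before database lock. The downside is that a few late or lower-exposure scans stay in, so the estimated reduction may be slightly less favourable.

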5.3.4 Sensitivity Analyses for Primary Endpoint

Impact of COVID-19

The following sensitivity analyses will be performed to evaluate the impact of the COVID-19 pandemic:

- Vary threshold on the number of missed doses due to the pandemic in the definition of "substantial reduction in drug exposure" ICE. The "substantial reduction in drug exposure" ICE is defined with a threshold of ≥ 4 dose- months. A sensitivity analysis will be performed using different thresholds: 1, 2, 3, 5, and 6 dose-months. All other aspects of the primary estimator remain the same.
- Ignore COVID-19 impact on missed doses. A sensitivity analysis will be performed where all available data points will be used, irrespective of whether or not a "substantial reduction in drug exposure" ICE occurred or not.

5.3.5 Supplementary Analyses for Primary Endpoint

The number and proportion of participants with values below or equal to the positivity threshold will be summarized for each assessment time point. CL zero is the mean amyloid burden for a typical population of young healthy controls, and 100 CL is the typical mean of a population with AD. The CL value of 24 is consistent with the diagnostic amyloid positivity threshold (Klunk et al. 2015; Navitsky et al. 2018) and will be used for the CL variable as defined for the primary analysis (see Section 5.3.2).

In order to account for the potential impact of missing values, a completers analysis will be performed, i.e., restricting the analysis at each visit to participants who completed the visit with non-missing data.

5.3.5.1 Subgroup Analyses for Primary Endpoint

The analysis of the primary endpoint will be repeated for subgroups of participants who received no home administrations of study drug by their study partner vs participants who received at least 1 home administrations by their study partner. The threshold of 1 administration may be varied for additional exploratory, data-driven analyses.

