- No new safety signals have been identified from the ongoing Phase III studies with gantenerumab with doses of up to 510 mg Q2W, which supports the safety of continued administration of gantenerumab uptitrated to the target dose in the current and planned studies, including Study WN29722. A higher ARIA risk is not expected in Study WN29722 compared with the Q2W regimen in the ongoing Phase III studies because the Q1W regimen will provide the same gantenerumab exposure with a lower C_{max} . The Sponsor's Internal Monitoring Committee (IMC) will evaluate safety data on a regular basis, including the incidence and nature of adverse events, serious adverse events, adverse events of special interest, ARIA-E, ARIA– hemosiderin deposition (ARIA-H), and ISRs and will make appropriate recommendations (see Section 3.1.2).
- Study WN29722 will provide the opportunity to enable an additional dosing regimen (i.e., a single injection of 255 mg SC Q1W), which will benefit individuals who prefer this approach.
- The overall risk of compromising the study effectiveness by introducing flexible care options, including home administration by study partners (non-professional caregivers), is deemed to be low. Mitigations are put in place to closely monitor and control the proper administration of the medication throughout the study. These include caregiver training, physician assessment, and investigators' checks. The

benefit is to provide a convenient option of home administration for the caregivers and the patients who would like to take advantage of this opportunity.

- Based on its mechanism of action, there is no reason to believe that gantenerumab administration would compromise the immunologic reaction of the body. This is supported by the nonclinical and clinical data collected through the development program of gantenerumab, where there has been no indication that gantenerumab administration compromised immune system or made individuals more susceptible to infections. Thus, there are no data or biological rationale suggesting that gantenerumab administration could increase the risk of infection by severe acute respiratory syndrome coronavirus 2 or more severe coronavirus disease 2019 (COVID-19) outcomes. Whereas people with AD, because of advanced age, may be in a higher-risk group for COVID-19, participation in Study WN29722 is not expected to increase that risk.

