3. SAMPLE SIZE DETERMINATION

Determination of sample size is relative to the sample of participants assessed by amyloid PET imaging using florbetaben. The sample size for this study is determined as the number of participants needed for the estimated change from baseline to Week 104 in amyloid PET load to fall into a 10 CL confidence interval (CI) around its true value. With a standard deviation of 25.67 CL (see below), 150 participants are required to fulfill this criterion. However, due to a lower than expected screen failure rate at the end of the enrollment period, a total of 192 participants have been enrolled.

The standard deviation of amyloid reduction was estimated using amyloid PET data from the ongoing Studies WN25203 (hereafter referred to as “SCarlet RoAD”) and WN28745 (hereafter referred to as “Marguerite RoAD”) open label extension (OLE) periods (based on a cutoff date of 14 October 2019), yielding a value of 25.67 CL.

Uncertainties of the parameters affecting the estimation (e.g., drop-out rate, study drug discontinuation rate, and standard deviation) were assumed to be equivalent to a decrease in sample size of up to around 35% and were corrected for accordingly. This drop-out rate is calculated based on Marguerite RoAD OLE at Week 104 that was ongoing at the time the study protocol was written. A sample size increase may be considered if factors external to the study would warrant a change to the sample size assumption.

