5.1 GENERAL CONSIDERATION

In the following sections, for all continuous variables for which descriptive statistics are indicated, the following statistics will be reported: the number of observations, the mean, median, standard deviation, and minimum and maximum. The 25th and 75th percentiles (Q1 and Q3) will also be reported for selected tables. Descriptive summaries of discrete data will include frequencies expressed in terms of number and percentage of participants.

For safety endpoints, the baseline is defined as the last available assessment prior to first study drug intake. For all other assessments, the baseline is defined as the last available assessment before or on the day of first study drug intake, unless specified otherwise.

All PD analyses and all clinical efficacy analyses will be performed on the ITT analysis set, unless specified otherwise. Safety analyses will be performed on the SE analysis set, except for analyses of MRI findings which will be performed on the M-SE analysis set and analyses of home administrations by study partner that will be performed on the SE, OH-SE, or H-SE analysis sets, as appropriate.

All analyses will be purely descriptive or exploratory without any formal hypothesis testing. For exploratory tests, a two-sided significance level of 5% will be used.

In general, missing outcome data will not be replaced or imputed unless specified otherwise. Number and percentage of missing data points will be reported for each visit for key endpoints of interest.

In statistical models using change from baseline of a given outcome measure as the dependent variable, participants with missing baseline outcome measure will be

Gantenerumab—F. Hoffmann-La Roche Ltd

Statistical Analysis Plan: WN29722 (GRADUATION)

18

Clinical Study Report: gantenerumab - F. Hoffmann-La Roche Ltd

Protocol Number: WN29722

Report Number: 1117435

18

excluded from the analysis. There will be no imputation of baseline value for outcome measures.

The impact of the COVID-19 pandemic on the study and its conduct will be monitored and the overall impact will be assessed and described in the Clinical Study Report.

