Descriptive tables will summarize the number of home administrations by study partner per participant as well as the reasons for the study partner not performing home-administrations. Reasons for switches in the person administering the study drug will be summarized as well. Graphical representations may be used to show the proportion of participants receiving administrations at home by study partner over time or to visualize the administrations by their study partner vs by a healthcare professional at home or at the site over time. The change from baseline in amyloid burden will be summarized as described in Sections 5.3.5.1 and 5.3.3 for participants who have had at least one home administration by their study partner vs those who have had none. These tables and figures will be based on the SE analysis set.

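### The amyloid comparison by study-partner home dosing yields two separately fitted subgroup means, with no between-group difference, no interval for it and no baseline adjustment between the groups

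*SAP*

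**What the plan says.** SAP 5.3.5.1, placed under the supplementary analyses, reads: "The analysis of the primary endpoint will be repeated for subgroups of participants who received no home administrations of study drug" by their study partner, against those who received at least one. It allows the cut-off of one dose to be varied in data-driven work. SAP 5.4 returns to the comparison: change in amyloid is summarised "for participants who have had at least one home administration by their study partner vs those who have had none", by cross-reference to 5.3.5.1 and 5.3.3.

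The analysis being repeated is the MMRM of SAP 5.3.3. It adjusts for visit, APOE ε4 status, baseline CL and baseline CL-by-visit, and reports least squares means at Weeks 52 and 104 with 95% CIs. SAP 5.3.3 runs it on the ITT set, whereas 5.4 places the home-dosing tables on the safety-evaluable set.

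SAP 2 and 5.1 say that no hypotheses are tested and that all analyses are descriptive or exploratory. SAP 5.1 adds: "For exploratory tests, a two-sided significance level of 5% will be used". No test is attached to 5.3.5.1. On the background judgement, Protocol 1.3.2 has a sentence beginning "The overall risk of compromising the study effectiveness by introducing flexible care options", names study-partner home administration among those options, and rates the risk as low.

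**The concern.** Protocol 3.1.1 makes the feasibility of study-partner home dosing one of the things the trial evaluates. The other home-dosing outputs (SAP 5.4 and 5.6.8) cover questionnaire answers, administration counts, adverse events and medication errors. The subgroup table is the only planned look at whether amyloid removal differs by home dosing.

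Two things are weak about it. First, the question is about a difference, and the plan estimates two means. A CI for each mean does not state how large a loss the data leave open.

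Second, home dosing is not allocated at random. It depends on a willing and capable partner (Protocol 4.1.1) and on the investigator's view of suitability (Protocol 4.3.2.1). The groups may therefore differ at baseline. When models are fitted separately, each least squares mean is usually evaluated at that subgroup's own average baseline CL. The baseline term then sharpens each mean but does not make the two comparable, so a baseline imbalance can look like an effect of home dosing or hide one.

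**Working it through.** **Inputs from the documents.** SD of the Week 104 change 25.67 CL; enrolled 192; a loss "assumed to be equivalent to a decrease in sample size of up to around 35% and were corrected for accordingly" (SAP 3); two-sided 5% for exploratory tests (SAP 5.1); predicted mean reduction 67 CL at Week 104 (Protocol 3.3.5).

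**Assumed, because the documents give no figure.** The no-home share (range shown); a benchmark difference of 0.5 SD = 0.5 × 25.67 = 12.8 CL, about 19% of 67 CL; baseline SD 30 CL; slope of change on baseline 0.3 to 0.5 CL per CL; a 10 CL baseline imbalance.

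**The plan's own figure.** SAP 3 wants the estimate "to fall into a 10 CL confidence interval (CI) around its true value" and says: "With a standard deviation of 25.67 CL (see below), 150 participants are required to fulfill this criterion". Reading this as a 95% CI of total width 10, n = (1.96 × 25.67 / 5)² = 101.3, so 102. Dividing by 0.65 gives 157, not 150. A loss of 32% gives 150 exactly (102 / 0.68), which is compatible with a loss described as up to around 35%, so I do not call it an error. With 192 enrolled, 192 × 0.65 = 124.8 evaluable and the half-width is 1.96 × 25.67 / √124.8 = 4.5 CL. The study is sized for one overall mean, not for a contrast between groups.

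**Precision of the difference.** Unadjusted half-width = 1.96 × 25.67 × √(1/n₁ + 1/n₂). The miss rate is one minus the power of a two-sided 5% two-sample t-test (noncentral t) for a true 12.8 CL difference.

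| Evaluable | No-home share | n₁ vs n₂ | Half-width (CL) | Miss rate |
|---|---|---|---|---|
| 125 | 50% | 62 vs 63 | 9.0 | 21% |
| 125 | 30% | 38 vs 87 | 9.8 | 28% |
| 125 | 20% | 25 vs 100 | 11.3 | 40% |
| 125 | 10% | 12 vs 113 | 15.3 | 63% |
| 192 | 50% | 96 vs 96 | 7.3 | 7% |
| 192 | 20% | 38 vs 154 | 9.1 | 22% |
| 192 | 10% | 19 vs 173 | 12.2 | 46% |

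Covariates would help. If they explained 10 to 30% of the variance (assumed), the 21% would fall to about 16 to 8%.

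**Effect of separate fits.** With each mean taken at its own subgroup's baseline average, the apparent difference in the absence of any home effect is slope × imbalance: 0.3 × 10 = 3 CL, and 0.5 × 10 = 5 CL. I simulated 25 vs 100 participants with baseline SD 30, total SD of change 25.67 and no home effect:

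- Separate fits gave spurious differences of 2.9 CL (slope 0.3) and 5.0 CL (slope 0.5). A 5% comparison of the two means rejected in about 12% and 25% of runs.
- One joint model with group and baseline gave about 0 CL and about 5%.

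**The case against.** The strongest reply is that this is an exploratory supplementary table. The SAP tests no hypothesis, ties no test to this subgroup, and nowhere says that similar means will be taken to show that home dosing preserves the effect. That stands. A reader might infer that a conclusion of no difference is planned, but the documents do not say so. The low-risk judgement in Protocol 1.3.2 rests on training, physician assessment and investigator checks, not on this table.

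A reader might also take 21% as the least possible miss rate. It is not. It needs the full 35% loss, which the SAP gives only as an upper figure pooling drop-out, discontinuation and SD uncertainty. It also needs no gain from covariates. With all 192 evaluable and equal groups the rate is about 7%. The 0.5 SD benchmark is mine, since the plan sets no margin.

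Three further points count against the concern:

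- Each subgroup mean does carry a 95% CI, so a reader could combine the two into an approximate CI for the difference. That CI would still lack baseline adjustment.
- SAP 5.6.8 summarises baseline characteristics for these same two groups, and the descriptive part of 5.3.3, if repeated, shows baseline CL. An imbalance would be visible, though not corrected.
- The simulated artefact of 3 to 5 CL is well inside the ±11 CL half-width at that split, and its inputs are assumed.

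The descriptive label does not settle the matter, because a difference with its CI is itself descriptive and SAP 5.3.3 already reports CIs. A joint model would not remove confounding by the other reasons a participant is or is not dosed at home.

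**Conclusion.** The point holds as a weakness of method in an exploratory analysis. The only planned amyloid comparison by study-partner home dosing reports two means and not their difference, and it gives up the between-group baseline adjustment that the sponsor's own model could supply. This second part rests on reading the repeated analysis as separate fits and on the usual convention for least squares means; the SAP does not state the reference point.

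The spurious difference of about 3 to 5 CL is conditional on the assumed slope and imbalance. The uncertainty in the difference is about ±9 to ±15 CL at 125 evaluable and ±7 to ±12 CL at 192, over no-home shares of 50% to 10%. The matching miss rates for 12.8 CL are about 21 to 63% and 7 to 46%. Eligibility normally requires a partner able to inject, so an equal split looks optimistic, but the documents do not give the share. The primary Week 104 estimate is untouched.

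**What to change.** In SAP 5.3.5.1, and by reference in 5.4, replace the two separate fits with one MMRM on one stated analysis set, settling the ITT and safety-evaluable wording. Keep the existing terms and add home-dosing group and group-by-visit. Report the adjusted difference (at least one study-partner home dose minus none) at Weeks 52 and 104 with its 95% CI. Label it exploratory and non-randomised, with residual confounding acknowledged. State that a CI including zero will not be read as evidence that home dosing causes no loss of amyloid reduction.

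The cost is SAP wording, one model and one table, with no new data. The drawback is a visibly wide CI, which makes the statement on home dosing more cautious.
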